### **B. Statistical Considerations**

# **Sample Size Justification**

Our sample size calculation is based on data from Boston IVF from 2013 to 2018 for patients with less

than 3 million total motile sperm post prep for IVF/ICSI patients. The mean number of total motile sperm is 38 million  $\pm$  24 which will be our control group. We hypothesize that the mean number of total motile sperm at the time of retrieval will increase to 48 million. In order to achieve 80% power to detect the specified difference using a two-sided alpha of 0.05, we will need 90 evaluable participants per arm. We anticipate that approximately 15% of participants will drop out or crossover, and we will inflate the sample size by another 15% to account for a non-normal distribution. Thus, we aim to randomize 117 participants per arm for a total of 234 participants.

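### The two 15% allowances are added (90 x 1.30 = 117) when a loss and an inflation should be compounded to 122 per arm; a minor shortfall, leaving about 78% power if both are used in full

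*Combined protocol and SAP*

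**What the plan says.** All the figures are in the combined protocol and SAP, section B3.B, Sample Size Justification.

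- Control arm: "The mean number of total motile sperm is 38 million", with a spread of 24.
- Intervention arm: "We hypothesize that the mean number of total motile sperm at the time of retrieval will increase to 48 million".
- Error rates: "In order to achieve 80% power to detect the specified difference", "using a two-sided alpha of 0.05".
- Base number: "we will need 90 evaluable participants per arm".
- First allowance: "We anticipate that approximately 15% of participants will drop out or crossover".
- Second allowance: "we will inflate the sample size by another 15% to account for a non-normal distribution".
- Result: "Thus, we aim to randomize 117 participants per arm for a total of 234 participants".

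The section gives no formula for combining the two allowances, and does not say whether the second 15% applies to 90 or to a number already inflated. It also does not split the first 15% into dropout and crossover. The Data Analysis section commits to an intention-to-treat analysis and a per-protocol analysis, and lets the data distribution decide between parametric and non-parametric tests.

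**The concern.** The two allowances do different jobs. The non-normality allowance raises the number that must be available for analysis. The dropout allowance is a share of the participants randomised, so the evaluable target has to be divided by 0.85; adding 15% to it is not enough. Summing two percentages on the base of 90 undersizes the trial relative to the plan's own assumptions.

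At stake is whether the stated power belongs to the stated enrolment. Anyone interpreting a null result would rely on the 80%, and this section is the only place where it is derived.

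**Working it through.** **Inputs** (all from the Sample Size Justification): difference 48 - 38 = 10 million; SD 24, reading the stated spread as a standard deviation common to both arms; two-sided alpha 0.05; power 80%; base n 90; loss 15%; non-normality inflation 15%. Allocation is 1:1 (Randomization section).

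**1. The base number.** n = 2 x [(1.96 + 0.8416) x 24 / 10]^2 = 90.4 per arm by the normal approximation, and 91.4 by the t-test. The plan's 90 reproduces, rounded down slightly. With exactly 90 per arm, power is 79.8% (normal) or 79.4% (t-test).

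**2. How 117 arises.** Ways of combining the allowances, starting from 90:

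| Rule | Per arm |
|---|---|
| 90 x (1 + 0.15 + 0.15) | 117.0 |
| 90 x 1.15 x 1.15 | 119.0 |
| 90 / 0.85 + 13.5 | 119.4 |
| 90 x 1.15 / 0.85 | 121.8 |
| 90 / 0.85 / 0.85 | 124.6 |

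Only simple addition gives 117.

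**3. What the allowances require.** Evaluable target: 90 x 1.15 = 103.5. Randomised: 103.5 / 0.85 = 121.8, so 122 per arm (244 in total). This is 5 per arm more than planned, or 4.3% above 117.

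**4. What 117 delivers if both allowances are used in full.** Evaluable: 117 x 0.85 = 99.45, against 103.5. Effective number after the non-normality allowance: 99.45 / 1.15 = 86.5.

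Power (normal) = Phi[(10/24) x sqrt(86.5/2) - 1.96] = Phi(2.74 - 1.96) = 78.2%. The t-test gives 77.8%.

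Difference detectable with 80% power (normal) = 2.8016 x 24 x sqrt(2/86.5) = 10.2 million. The t-test gives 10.3 million.

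**5. Splitting the shortfall.** Rounding the base down to 90 accounts for 0.2 points (normal) or 0.6 points (t-test). Adding instead of compounding accounts for 79.8 - 78.2 = 1.6 points, or 79.4 - 77.8 = 1.6 points. At 122 per arm the effective number is 122 x 0.85 / 1.15 = 90.2, and power returns to 79.9% (normal) or 79.5% (t-test), which is the plan's own level.

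**6. If non-normality costs nothing.** 99.45 evaluable per arm gives 83.6% (normal) or 83.2% (t-test).

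**7. Crossovers kept in the intention-to-treat analysis.** The documents give no split of the 15%, so these cases are assumptions. Each takes a crossover to have the other arm's mean, counts the non-normality allowance in full and uses the normal approximation.

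- No dropout, 5% crossing over in each arm: n = 117 / 1.15 = 101.7, difference 10 x (1 - 0.10) = 9.0 million, power 76%.
- No dropout, 7.5% crossing over in each arm (or 15% in one arm only): difference 8.5 million, power 71%.
- 10% dropout and 5% crossover in each arm: n = 117 x 0.90 / 1.15 = 91.6, difference 10 x (1 - 2 x 0.05/0.90) = 8.9 million, power 71%.

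**The case against.** The strongest reply is that nothing in the section contradicts itself. It ties the power to 90 evaluable participants, it prescribes no compounding rule, and after a full 15% loss 117 still leaves 99. On that view the non-normality margin is only a cushion, the Data Analysis section leaves open whether a non-parametric test will be used at all, and power is about 83%. This stands in part: the shortfall appears only when the non-normality allowance is counted in full. But the plan adds that allowance as something needed, and it cannot also be spent on dropout.

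A second reply is that the size is negligible. The 15% is itself approximate; multiplying twice by 1.15 gives 119 to 120, close to 117; and an SD of 24.5 instead of 24 would lower power at 90 per arm by about as much (to 78.2% normal, 77.7% t-test). The smallness is conceded. Multiplying twice still treats a loss as an add-on, though: 120 x 0.85 = 102, short of 103.5.

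A third reply is that crossovers stay in the intention-to-treat analysis, so 0.85 overstates the loss of participants. If only 10 of the 15 points were true loss, 91.6 effective per arm would remain, above 90. The head count is right, but it does not rescue 117: the remaining 5% dilute the difference, and step 7 puts power at about 71% in that case.

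A reader might go further and infer that the trial is materially underpowered, or that 117 cannot give 80% power under any reading. The documents do not support either. The addition costs about 1.6 points, and with no non-normality penalty and no dilution from crossovers the power exceeds 80%. A reader might also put the requirement at 125 per arm. That figure comes from replacing the base of 90 with the t-test value of 92 (92 x 1.15 / 0.85 = 124.5), which is a separate rounding matter.

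**Conclusion.** The point holds as a minor arithmetic correction. The two allowances were added; taken as the plan describes them, they require 122 per arm. With 117 per arm and both used in full, power for 38 versus 48 million is about 78%, against 79.4% to 79.8% for the plan's own 90.

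This rests on three readings: the spread of 24 is a common SD, the 15% loss is a share of those randomised, and the non-normality allowance represents a real need for 15% more evaluable participants. That the allowances were added is inferred from the exact match with 117, since no formula is given.

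For the intention-to-treat analysis, 78% is an upper limit when the full 15% drop out or cross over and non-normality takes its full share, because a retained crossover costs more power than a dropout. It is not a limit if fewer participants are lost or cross over. The size of the dilution cannot be fixed from the documents, and it is a separate and potentially larger question than how the allowances combine.

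**What to change.** In the Sample Size Justification, show the combining formula, n x 1.15 / 0.85, and replace the unconditional power statement with one that carries its conditions. For example: with 234 randomised, power is about 78% for 38 versus 48 million (SD 24), or 80% for a difference of about 10.2 to 10.3 million, if all 15% are lost and the non-normality allowance is fully used; this is an upper limit under those allowances for the intention-to-treat analysis, because crossovers kept in it dilute the difference.

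The cost is one sentence and a slightly less favourable stated power. No extra enrolment is needed, and the conduct and analysis of the trial do not change.

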# **Data Analysis**

We will conduct both intention-to-treat and per-protocol analysis. Both intention-to-treat and per-protocol analyses are noted in the RCT reporting guidelines (CONSORT) as valid approaches. For this study, we will perform an intention-to-treat analysis because it is the gold standard for RCTs, even with crossover or withdraw. We also will perform a per-protocol analysis. While this analysis can introduce bias, it is a valid statistical approach.

Descriptive data will be presented as a proportion, mean with standard deviation or median with interquartile range. Comparisons will be made using Chi-square or Fisher's exact test for categorical variables and parametric or non-parametric tests for continuous variables based on data distribution. Log-binomial regression will be used to estimate risk ratios and 95% confidence intervals for the primary and secondary outcomes. While we anticipate that randomization will balance the distribution of measured and unmeasured potential confounders in the two study arms, if this is not the case, we will assess the influence of potential confounders as needed. All data will be analyzed with SAS 9.4 (SAS Institute Inc., Cary, NC, USA). All tests will be two sided and a P value <0.05 will be required to confer significance.

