The semen sample provided on day of oocyte retrieval will be analyzed with a basic and advanced semen panel. Any remaining samples will be discarded per routine practice. Prior to providing the semen sample, participants turn in the completed survey/ejaculation history calendar to a member of the research team. Blank copies will be available for participants the day of egg retrieval if needed.

There is no clinical risk to your IVF cycle as the procedures followed are standard clinical practice. Study participation will not influence any element of the IVF treatment except for EA counseling. Currently there is no set protocol on how EA counseling is performed. Counseling on EA varies among the medical care teams at Boston IVF as some patients may or may not receive explicit EA instructions. Patients may be counseled by the medical care team with recommendations to abstain for > 48 hours at the time of their consult. All patients in this study are using ICSI to fertilize eggs and the number of sperm needed for treatment will not be compromised by ejaculatory abstinence < 24 hours. Participants who crossover to the alternate treatment arm will continue their participation in the study so that we can collect cycle outcome data. IVF stimulation protocols will be according to standard practice. ICSI and embryology practice will follow standard practice. Selection of embryos will be based on the current embryology laboratory selection protocols or by preimplantation genetic testing for aneuploidy (PGT-A). The number of embryos transferred will be based on the usual American Society of Reproductive Medicine guidelines. Any unused embryos will be disposed of or cryopreserved per

standard clinical protocols.

Outcomes

*Primary:* Total motile sperm (motility x concentration x volume)

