# Secondary:

Clinical data from the IVF cycle randomized to intervention or control condition, will include but not be limited to the following: fertilization rate; blastocyst rate; number of morphologically normal blastocysts; number of euploid and aneuploid embryos (if preimplantation genetic testing-aneuploidy [PGT-A] performed); number of embryos transferred; implantation rate; biochemical pregnancy rate (defined as positive beta-hCG but no gestational sac visualized); clinical pregnancy rate (defined as confirmation of gestational sac on ultrasound); ongoing pregnancy rate (defined as confirmation of a gestational sac with at least one fetal pole with a fetal heartbeat); live birth rate (defined as delivery > 23 weeks gestation); Cumulative pregnancy rate; Miscarriage rate; Multiple pregnancy, defined as twins or higher-order gestations

Semen characteristics will be examined in relation to: Changes in semen analysis from baseline diagnostic sample An advanced semen analysis panel Time from last ejaculation to oocyte retrieval

All data that is collected for the trial is clinical data that would be collected and stored in the electronic medical record as part of routine clinical care. In addition to collecting outcome data from this initial IVF cycle, we will collect data regarding subsequent IVF cycles and outcomes for any of the frozen embryos created but not transferred in this cycle.

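### The only effect measure and confidence interval method in the plan is a log-binomial risk ratio, which cannot be applied to the continuous primary outcome, total motile sperm

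*Combined protocol and SAP*

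**What the plan says.** The Outcomes paragraph under Methods (section B3) makes total motile sperm the primary outcome and defines it as motility times concentration times volume.

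The Sample Size Justification treats it as a mean. For the control group, "The mean number of total motile sperm is 38 million", with 24 after the plus/minus sign. For the short-abstinence arm, "We hypothesize that the mean number of total motile sperm at the time of retrieval will increase to 48 million". The text also anticipates skewed data: "we will inflate the sample size by another 15% to account for a non-normal distribution".

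The Data Analysis section has three relevant sentences:

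- Summaries: "Descriptive data will be presented as a proportion, mean with standard deviation or median with interquartile range".
- Tests: "parametric or non-parametric tests for continuous variables based on data distribution".
- Estimation: "Log-binomial regression will be used to estimate risk ratios and 95% confidence intervals for the primary and secondary outcomes".

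The third is the only sentence in the plan that names a between-arm effect measure or a method for a confidence interval, and it names the primary outcome explicitly.

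**The concern.** Log-binomial regression models the probability of a binary event. Total motile sperm is measured in millions, and the plan never turns it into an event. As written, the estimation method for the main result cannot be carried out.

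What is at stake is the reported size of the effect and its interval. Once the risk ratio is ruled out, the analyst has to choose a replacement, and nothing in the plan prevents that choice from being made after the data are seen. The choice is a real one. The plan expects non-normal data and leaves the test to depend on the observed distribution. A t-test goes with a difference in means, while a rank test goes with a different quantity. Following the sentence literally would require a cut-off, and both the risk ratio and the power would then depend on an unstated number.

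The sentence also reaches the count outcomes in the secondary list: "number of morphologically normal blastocysts; number of euploid and aneuploid embryos", and the number of embryos transferred. A risk ratio does not describe these either.

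**Working it through.** **1. Was the primary outcome planned as continuous?** Inputs from the Sample Size Justification: means 38 and 48 million, so a difference of 10; SD 24 (the figure after the plus/minus sign, taken as common to both arms); two-sided alpha 0.05; power 80%.

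- n per arm = 2 × ((1.960 + 0.842) × 24 / 10)² = 90.4, against the stated 90.
- Power at 90 per arm = 79.8% (normal approximation) or 79.4% (t-test).
- 90 × 1.30 = 117, the stated number to randomise per arm.

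The plan's figures are reproduced by a two-sample comparison of means.

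**2. Is there a binary version anywhere?** The Outcomes text gives none. The Inclusion Criteria mention fewer than 10 million motile sperm (unprocessed) and fewer than 3 million (processed), but these decide who enters the trial. They do not define success at retrieval.

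**3. Does another sentence supply an effect measure?** The testing sentence gives a test without an estimate or interval. Means with SDs and medians with interquartile ranges are summaries within each arm, not a comparison between arms.

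**4. What a fitting measure would deliver.** For the difference in means at 90 per arm, the 95% half-width is 1.973 × 24 × √(2/90) = 7.06 million. The expected interval is about 2.9 to 17.1 million.

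**5. Do the candidate measures differ?** Assume a lognormal shape, for which median = mean / √(1 + CV²).

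- SD 24 in both arms: the ratio of means is 48/38 = 1.26, but the ratio of medians is 1.34.
- Equal CV (24/38): the difference in means is 10 million, but the difference in medians is 8.5 million.

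**6. Illustration only: a risk ratio obtained by cutting the outcome.** The plan does not propose this; the cut-offs and shapes are assumptions. Under normality, P(above c) = 1 − Φ((c − mean)/24):

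| Cut-off (million) | >48 h arm | <24 h arm | Risk ratio |
|---|---|---|---|
| 20 | 0.773 | 0.878 | 1.14 |
| 38 | 0.500 | 0.662 | 1.32 |
| 60 | 0.180 | 0.309 | 1.72 |

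The next table covers all cut-offs from 20 to 60 million in steps of 1, with 90 per arm and a two-proportion test using pooled null variance:

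| Assumed shape | Risk ratio | Power |
|---|---|---|
| Normal, SD 24 | 1.14–1.72 | 46–60% |
| Lognormal, equal CV | 1.12–1.78 | 42–57% |
| Lognormal, SD 24 in both arms | 1.19–1.70 | 39–92% |

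Power is not lost under every assumption. The risk ratio simply has no determinate value until a cut-off is stated.

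**7. Does the proposed replacement behave under skew?** In 10,000 simulated trials with 90 per arm, the unequal-variance 95% interval for the mean difference covered 10 million in 94.9% (normal), 95.5% (lognormal, equal CV) and 94.9% (lognormal, SD 24) of trials.

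**The case against.** The best reply is that this is loose drafting with little practical effect. The testing sentence just before already sends continuous variables to a suitable test, the sample size rests on a difference in means, and nobody could fit a log-binomial model to raw sperm counts without noticing. The authors probably meant the pregnancy and live-birth outcomes. On that reading the hypothesis test, the sample size and the conduct of the trial are untouched, and the choice of estimate is narrower than it looks. Most of this is fair, and it limits the seriousness of the point. It does not remove it: correcting the slip still leaves the primary outcome without a named estimate or interval, and a sample-size assumption is not an analysis specification.

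A second reply is that the dichotomised figures measure no expected harm, since no cut-off is proposed. That is also fair. They are illustrative and the conclusion does not rest on them.

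A third concerns the remedy. With skewed data a comparison of means may have less power than the rank test the plan already permits. Simulation at 90 per arm (4,000 trials) gave, for the unequal-variance t-test versus the rank test, 80% versus 78% (normal), 70% versus 74% (lognormal, equal CV) and 78% versus 94% (lognormal, SD 24). These shapes are assumed, but the point is worth weighing. It is a reason to consider a log-scale measure, provided that it is fixed in advance; it is not a reason to leave the measure open.

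**Conclusion.** The concern holds. The one effect measure and interval method the plan names is assigned by name to a continuous outcome, for which it is undefined. This is an error in the text as it stands, not merely missing detail.

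It should be corrected, but it does not invalidate the trial, because a valid hypothesis test remains available and the sample size reproduces. What is unspecified is the main reported result: on the plan's figures, a difference of 10 million with a 95% interval of roughly ± 7.1 million.

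That the method does not fit follows from the text alone. The interval width assumes the plan's SD of 24 in both arms and 90 evaluable participants per arm. The risk-ratio, power and median figures additionally assume the distributions and cut-offs stated with them.

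**What to change.** Revise the Data Analysis section in three places.

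1. **Binary outcomes.** Limit log-binomial regression to per-patient binary outcomes and list them: for example clinical pregnancy, ongoing pregnancy and live birth. Biochemical pregnancy, miscarriage and multiple pregnancy can be added once their denominators are stated.
2. **Primary outcome.** Name one analysis of total motile sperm: the difference in means (<24 h minus >48 h) with an unequal-variance or bootstrap 95% confidence interval and the matching two-sided test. This agrees with the sample-size basis. A ratio of geometric means from a log-scale model is an acceptable alternative, and may suit skewed data better, but one of the two must be chosen before any outcome data are examined.
3. **Other secondary outcomes.** Analyse the blastocyst and embryo numbers with a count model or a continuous comparison. For fertilization, blastocyst and implantation rates, state the unit of analysis and choose the method accordingly.

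The cost is a few sentences of analysis text, with no extra patients or data. If the investigators do want a risk ratio for the primary outcome, they would need to define the cut-off in advance and redo the sample size for a comparison of proportions.

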# Randomization

We will use computer-generated block randomization in REDCap to randomize participants in a 1:1 ratio to the EA period more than 48 hours (routine care) or less than 24 hours. Randomization will be stratified by whether the patients receive PGT-A. Research staff will call participants on stimulation day 6 to 8 to notify participants which treatment arm they were randomized to. The participant can withdraw from the study at any time if desired or will have an opportunity to not continue with the treatment arm they were randomized to. We anticipate that most of the crossovers will occur due to participants wishing to be in the alternate EA period or not being able to produce a sample in the window assigned.

The purpose of this study is to examine semen parameters with IVF/ICSI when male factor infertility patients abstain from ejaculation more than 48 hours (routine care) or less than 24 hours. Information from this study would allow us to provide evidence-based recommendations to future patients who need IVF/ICSI.

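### Log-binomial regression is named for fertilization and blastocyst rates without a unit of analysis or any allowance for clustering within couple

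*Combined protocol and SAP*

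**What the plan says.** The Data Analysis section assigns one regression model to everything: "Log-binomial regression will be used to estimate risk ratios and 95% confidence intervals for the primary and secondary outcomes". Its other methods are simple comparisons: "Comparisons will be made using Chi-square or Fisher's exact test for categorical variables", and "parametric or non-parametric tests for continuous variables based on data distribution". Every test is two-sided at the 5% level, with no distinction between outcomes.

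The secondary outcome list includes "fertilization rate; blastocyst rate; number of morphologically normal blastocysts" and, further on, "number of embryos transferred; implantation rate". It defines no denominator for any of these rates. The same list holds outcomes that occur at most once per couple in the index cycle, such as clinical pregnancy and live birth.

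The Randomization section uses blocks "to randomize participants in a 1:1 ratio", stratified by use of PGT-A, so the randomized unit is the participant and hence the couple. Nowhere does the plan mention clustering, GEE, robust variance, random effects or a per-couple summary.

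**The concern.** A log-binomial model needs a yes/no unit, or events out of trials. For fertilization rate that unit is the oocyte; for blastocyst rate it is the oocyte or embryo. Units from one couple share a semen sample and an egg source, so their outcomes are likely to be positively correlated. The ordinary log-binomial variance ignores this, and so do chi-square and Fisher tests applied to pooled oocytes.

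The result would be standard errors that are too small and chance differences declared significant too often. These two rates form the link between abstinence and embryo development, and section B4 expects that the findings may alter practice. A spurious difference here would therefore be read as meaningful.

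The counts of normal blastocysts and of euploid embryos are a related case: a risk-ratio model does not fit a count.

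**Working it through.** **The plan's own figures.** The plan gives no figure for oocyte- or embryo-level outcomes. Its only calculation concerns total motile sperm. A difference of 10 million (48 − 38), SD 24, two-sided 5% and 80% power give an unrounded 90.4 per arm, against 90 stated. The randomized number is 90 × 1.30 = 117 per arm. This agrees closely and does not bear on clustering; 117 is used below as the number of couples per arm.

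**Assumed inputs (none is in the documents).** Units per couple *m*, within-couple correlation ρ, and event rates: fertilization, mean 10 oocytes and 70%; blastocyst, mean 7 units and 50%; implantation, mean 1.1 to 1.5 embryos transferred and 45%.

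**Step 1, formula with equal cluster sizes.** Design effect DE = 1 + (*m* − 1)ρ. Actual two-sided error = 2 × [1 − Φ(1.96/√DE)]. For example, *m* = 10 and ρ = 0.10 give DE = 1 + 9 × 0.10 = 1.90, √DE = 1.38 and an error of 15.5%.

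| ρ | DE, *m* = 8 | Error | DE, *m* = 10 | Error |
|---|---|---|---|---|
| 0.02 | 1.14 | 6.6% | 1.18 | 7.1% |
| 0.05 | 1.35 | 9.2% | 1.45 | 10.4% |
| 0.10 | 1.70 | 13.3% | 1.90 | 15.5% |
| 0.20 | 2.40 | 20.6% | 2.80 | 24.1% |

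**Step 2, simulation with varying numbers per couple.** Beta-binomial data with no treatment effect, 117 couples per arm, 6,000 trials per cell, unadjusted log risk ratio. The SE ratio is the correct standard error divided by the unadjusted one.

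| ρ | Fertilization: error | SE ratio | Blastocyst: error | SE ratio |
|---|---|---|---|---|
| 0.02 | 7.8% | 1.11 | 7.0% | 1.07 |
| 0.05 | 12.2% | 1.25 | 9.5% | 1.18 |
| 0.10 | 18.2% | 1.46 | 14.4% | 1.33 |
| 0.20 | 28.0% | 1.81 | 21.7% | 1.59 |

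With 90 couples per arm the fertilization errors are 7.6%, 11.8%, 18.8% and 27.8%, so the inflation hardly depends on the number of couples.

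**Step 3, implantation rate.** With 1.1 to 1.5 embryos per couple and 117 couples per arm, the error is 5.0% to 7.0% for ρ from 0.05 to 0.30, and at most 8.2% at ρ = 0.50. The clusters are too small for the correlation to matter much.

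**Step 4, remedies.** A standard error clustered on couple, or a t-test on one rate per couple, gave 4.2% to 5.6% across all the scenarios with 117 couples per arm.

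**The case against.** The strongest reply is that the plan never says oocytes are treated as independent. That is true: a reader might infer it from the model named, but the plan is silent on both the unit and the variance method. The model sentence also cannot be literal throughout, because it covers the primary outcome, which is continuous (a separate matter), and several counts. It may have been written with the once-per-couple pregnancy outcomes in mind, for which the model is sound. The continuous-variable tests already listed would be valid on one rate per couple.

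These points limit the claim but do not remove it. The continuous-variable tests do not produce the risk ratios and intervals promised for the secondary outcomes, and fertilization and blastocyst rates are not exempted. The plan therefore permits a valid and an invalid analysis of the same outcome, and the choice could be made after the data are seen.

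Two further points stand:

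- **Implantation rate does not belong with the other two.** A reader might group all three, but the plan says "The number of embryos transferred will be based on the usual American Society of Reproductive Medicine guidelines" and, with one or two embryos per transfer, the effect is small. It would grow only if several transfers per couple were pooled. The plan does state that "we will collect data regarding subsequent IVF cycles and outcomes for any of the frozen embryos created but not transferred in this cycle", but not that these are pooled into the rate.
- **The size rests wholly on assumptions.** At ρ = 0.02 the inflation is modest. A figure such as 34.4% for fertilization requires ρ = 0.30, and nothing in the documents establishes that value.

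**Conclusion.** The point holds for fertilization and blastocyst rates. Applied as named, the model works on units nested within the randomized couple, and nothing in the plan corrects for this. Over assumed correlations of 0.02 to 0.20 and about 7 to 10 units per couple, type I error is about 7% to 28% against a nominal 5%. Correct intervals, on the log scale, would be about 1.1 to 1.8 times as wide for fertilization and 1.1 to 1.6 times as wide for blastocyst rate. The direction follows from any positive within-couple correlation; the size cannot be fixed from the documents.

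The documents do not support the broader conclusion that the trial's main comparison is compromised. Total motile sperm is measured once per participant, the sample size rests on it alone, and once-per-couple outcomes in the index cycle are not clustered. This should be corrected before analysis, as a matter of secondary-outcome inference.

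**What to change.** In the Data Analysis section:

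- Define the denominator for fertilization, blastocyst and implantation rates.
- For fertilization and blastocyst rates, choose one of two routes in advance. Either estimate risk ratios with a log-link GEE clustered on couple with robust standard errors, or analyse one rate per couple with the continuous-variable tests already listed and drop the risk-ratio promise for these outcomes. The first weights couples by their number of units and the second weights them equally, so the choice should be stated.
- Treat implantation rate in the same way if more than one embryo or transfer per couple is counted.
- Include the PGT-A stratum as a covariate in the regression model, since randomization is stratified on it.
- Analyse blastocyst and euploid counts per couple with the parametric or non-parametric tests already listed.
- Keep the plain log-binomial model for binary outcomes recorded once per couple.

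The cost is a few sentences and, for the GEE, one REPEATED statement in PROC GENMOD in the SAS software already planned. No further participants or data are needed. The downside is wider, correct intervals for these secondary outcomes.
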